3.2 Number of Sites

This study will be conducted at approximately 5 sites in Germany and the Netherlands. Additional countries or sites may be added if necessary.

Sites that do not enroll subjects into an open cohort within 2 months of site initiation may be closed or replaced.

3.3 Number of Subjects

Participants in this clinical investigation shall be referred to as "subjects".

Approximately 78 subjects are planned for enrollment into this study. Approximately 39 subjects will be enrolled in the dose-escalation cohorts and approximately 39 subjects will be enrolled in the dose-expansion cohort of the study.

Based on emerging data, additional subjects may be enrolled.

The rationale for the number of subjects is provided in [Section 10.2](#).

3.4 Replacement of Subjects

A replacement subject who will be assigned to the same dose level may be enrolled if a subject is not DLT-evaluable in the dose-escalation cohorts. A DLT-evaluable subject is defined as receiving at least 90% of the planned doses of investigational product. Subjects in the dose-expansion cohort may be replaced if they discontinue from the study for reasons other than disease progression or toxicity.

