5.1 Treatment Assignment

An Amgen representative will notify the site(s) in writing when a cohort is open to screen new subjects. In the dose-escalation cohorts, subjects will be assigned sequentially into cohorts as they open. Three subjects will initially be enrolled into each dose-escalation cohort with at least a 48-hour interval between treatment start of subject 1 and subject 2 of each cohort. In the event that a DLT is observed, 3 additional subjects may be enrolled for a total of up to 6 evaluable subjects. Subjects are considered evaluable, for the purposes of the dose level review of safety information if they receive at least 90% of the planned doses of investigational product or if they have discontinued investigational product due to a DLT. Subsequent cohorts will begin enrollment upon completion of the previous cohort if it is deemed safe to proceed to the next dose level.

Subjects not participating in the Imaging Study will start enrollment into the dose-expansion cohort upon completion of the dose-escalation cohorts. Subjects concurrently participating in the Imaging Study will start enrollment into the dose-expansion cohort while dose-escalation cohorts are still open for enrollment.

The treatment start date is to be documented in the subject's medical record and on the enrollment eCRF.

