6.2.1.3 Dose-cohort Study Escalation and Stopping Rules Dose-limiting Toxicities (DLT)

A DLT will be defined as any of the following occurring in a subject during the first 28 days of treatment and regarded by the investigators and/or sponsor to be related to AMG 211. The Common Terminology Criteria for Adverse Events (**CTCAE** version 4.03) will be used to assess toxicities/adverse events.

Hematological DLTs

- ANC < $0.5 \times 10^9/L$ for ≥ 7 days
- Febrile neutropenia (fever of unknown origin without clinically or microbiologically documented infection) with ANC < $0.5 \times 10^9/L$ and fever $\geq 38.5^{\circ}\text{C}$
- Platelets < $25 \times 10^9/L$ ≥ 7 days

Non-hematological DLTs

Any AMG 211-related \geq grade 3 non-hematological toxicity excluding

- Nausea and vomiting, which is not refractory to anti-emetics
- Flare-up of pain because of potential increase in tumor volume is not regarded as a DLT
- Cytokine release syndrome manageable with symptomatic treatment and/or infusion interruption of up to 2 days

Subjects are evaluable for a DLT when they have received at least 90% of the planned doses of investigational product within the first treatment cycle (first 28 days of a cycle independent of length of the infusion) with or without the occurrence of a DLT in the 28-day safety observation period.

Any adverse event occurring outside the DLT window that is determined by the investigator to be possibly related to the investigational product, which is seen more frequently or more severe than expected or is persistent despite appropriate management, can be determined to be a DLT upon unanimous decision by the DLRT after review of the adverse event and all available safety data.

For certain toxicities such as laboratory abnormalities without a clear clinical correlation (eg, increase in serum lipase level without signs or symptoms of a clinical pancreatitis), a

discussion between the investigator and the sponsor may take place whether that adverse event should be assessed as a DLT.

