10.1.2 Analysis Sets

The analysis of all endpoints, unless noted otherwise, will be conducted on the Safety Analysis Set defined as all subjects that are enrolled and receive at least 1 dose of AMG 211.

The analysis of DLT will be restricted to DLT-evaluable subjects. The DLT window is 28 days for all cohorts and is independent of the length of the infusion. A subject is not DLT-evaluable if he/she drops out before completion of cycle 1 for reasons other than an adverse event related to the investigational product. Ineligible subjects may be replaced.

The PK Analysis Set will contain all subjects who have received at least 1 dose of the investigational product and have at least 1 PK sample collected. These subjects will be evaluated for PK analysis unless the number of data points required for analysis is not enough, or significant protocol deviations have affected the data, or if key dosing or sampling information is missing.

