10.4.2 Primary Endpoint

A modified TPI Bayesian model will be used in the dose-escalation cohorts to estimate the MTD based on the incidence of DLTs among DLT-evaluable subjects that occur during the DLT window. Refer to [Appendix E](#) for details of the TPI Bayesian model. The MTD target TPI is (0.20, 0.35), and TPIs of (0.35, 0.60) and (0.60, 1.00) are defined as excessive and unacceptable, respectively. After each cohort, the model's recommended MTD dose for evaluation is the dose with the highest probability of the target TPI, but with a less than 0.25 probability of an excessive or unacceptable TPI. Dose-expansion will enroll additional subjects to gain further clinical experience. A final model estimate of the MTD using AMG 211 cIV dosing will be obtained utilizing all DLT-evaluable subjects from the dose-escalation cohort. Subjects who are not AMG 211 naïve at the time of enrollment will not be DLT-evaluable. Dose expansion-cohort subjects who participated in the Imaging Study are not DLT-eligible and will be excluded from this analysis. The probability of each TPI and of a DLT will be summarized by dose along with the estimated dose-toxicity curve. In addition, a sensitivity analysis will be done using data from all subjects in both dose-escalation and dose-expansion cohorts who receive at least 90% of the planned doses of investigational product during Cycle 1.

Additional summaries and/or models may be investigated, if warranted, to evaluate DLTs or other safety outcomes overall or in relation to dose, for example, all or selected related treatment-emergent adverse events leading to treatment interruption and/or discontinuation by cycle of onset.

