1. INTRODUCTION

The purpose of this statistical analysis plan (SAP) is to provide details of the statistical analyses that have been outlined within the protocol for AMG 211 Study 20130354 dated 24 March 2014. The scope of this plan includes the interim analysis and the final analysis that are planned and will be executed by the Biostatistics department or designee unless otherwise specified eg, standard PK tables may be provided by PKDM.

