3.1.1 Dose Escalation Phase

The dose-escalation part of the study is aimed at determining the MTD, safety, tolerability, PK, and PD of AMG 211. Planned dose levels for the dose-escalation cohorts are as follows: 200, 400, 800, 1600, 3200, and 6400 µg/d. Alternative dose levels may be explored based on emerging data.

Subjects in cohort 1 of the dose-escalation cohorts will receive AMG 211 for 7 days followed by 21 days off treatment (cycle 1). After completing cycle 1, if no DLTs are observed, all subjects in cohort 1 will be allowed to continue treatment with the same dose of AMG 211, but the infusion duration will be 14 days followed by 14 days off treatment.

In the subsequent dose-escalation cohorts, AMG 211 will be administered at escalating doses in a 2 weeks on and 2 weeks off schedule. Based on the results, the Dose Level Review Team (DLRT) may choose to extend the infusion duration from 14 to 28 days (a 4 weeks on and 2 weeks off schedule) if the 14-day administration schedule has been well tolerated and the safety profile allows for a longer infusion duration, and no anti-tumor response has been observed in the 14-day administration schedule.

Moreover, the DLRT may decide to enroll in parallel into a cohort with a 28-day treatment duration or to prioritize one infusion schedule.

Dose escalation decisions will consider the incidence of DLTs among DLT-evaluable subjects that occur during the first 28 days of treatment. For definition of DLT-evaluable subjects, please refer to section 3.4 in the protocol.

A safety review of dose escalation is planned after all subjects in dose escalation have had the opportunity to complete 6 months of the treatment.

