7.3 Dose Escalation Analysis Set

The analysis of DLT will be restricted to DLT-evaluable subjects. The DLT window is 28 days for all cohorts and is independent of the length of the infusion. A subject is not DLT-evaluable if he/she drops out before completion of cycle 1 (defined as completed 90% of the planned dose in cycle 1) for reasons other than an adverse event related to the investigational product. This analysis Set will consist of all available data from all DLT-evaluable subjects, with subjects analyzed according to the treatment received initially as described for the Safety Analysis Set. Ineligible subjects may be replaced.

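### Protocol 3.4, 6.2.1.3 and the 10.4.2 sensitivity set apply a 90%-of-dose condition with no exception for a subject stopped by a DLT, which conflicts with 5.1, 10.1.2 and SAP 7.3

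*Protocol*

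**What the plan says.** Three places use dose received as the only condition.

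- Protocol 3.4: "A DLT-evaluable subject is defined as receiving at least 90% of the planned doses of investigational product". A subject in dose escalation who is not evaluable may be replaced at the same dose level.
- Protocol 6.2.1.3: "Subjects are evaluable for a DLT when they have received at least 90% of the planned doses of investigational product", counted in the first 28 days of the cycle. The sentence goes on to say that this applies whether or not a DLT is seen, so a DLT does not waive the dose condition.
- Protocol 10.4.2, sensitivity analysis: all subjects in both "cohorts who receive at least 90% of the planned doses of investigational product during Cycle 1". This set does not use the term DLT-evaluable. It is a separate set with the same filter.

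Three places contain an exception.

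- Protocol 5.1, for dose level review: 90% of planned doses "or if they have discontinued investigational product due to a DLT".
- Protocol 10.1.2: a subject is lost only by dropping out before cycle 1 is complete "for reasons other than an adverse event related to the investigational product".
- SAP 7.3: the same rule, where having finished the first cycle is "defined as completed 90% of the planned dose in cycle 1) for reasons other than an adverse event related to the investigational product". SAP 10.5.1.1 uses this set for the DLT model.

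SAP 3.1.1 adds: "For definition of DLT-evaluable subjects, please refer to section 3.4 in the protocol". The SAP was written for the "protocol for AMG 211 Study 20130354 dated 24 March 2014", whose section 3.4 is not in the documents.

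**The concern.** A DLT is a listed reason for interrupting the infusion (6.2.1.4.2) and for stopping treatment permanently (6.2.1.4.4). Subjects with a DLT are therefore the ones most likely to fall below 90% of planned dose. A dose-only condition can remove subjects because they had the event being counted, and their contribution is then biased toward fewer DLTs. DLT incidence is part of the primary endpoint, and the MTD is a primary objective.

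The sections with an exception also disagree among themselves. An early stop for a related adverse event that is not a DLT is evaluable under 10.1.2 and SAP 7.3 but not under 5.1. Protocol 10.1.2 asks for completion of cycle 1, while SAP 7.3 treats 90% of the dose as completion, although both give a 28-day DLT window.

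**Working it through.** **1. Who is affected.** 90% of a 14-day infusion is 0.9 × 14 = 12.6 days, and 90% of a 28-day infusion is 0.9 × 28 = 25.2 days. An uninterrupted 14-day infusion stopped by a DLT before about day 12.6 makes the subject non-evaluable under 3.4 and 6.2.1.3 and removes the subject from the 10.4.2 sensitivity set. The same subject is evaluable under 5.1, 10.1.2 and SAP 7.3. A DLT after that point already meets 90%.

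**2. The plan's own figures.** Protocol 10.2 gives a 49% to 73% chance of at least one DLT in 3 evaluable subjects at true rates of 20% to 35%. The formula 1 − (1 − p)³ gives 0.488 and 0.725, which agrees. For the Appendix E prior, numerical integration gives P(rate ≤ 0.60 at 200 µg/day) = 0.900 (stated 0.90) and P(rate ≤ 0.20 at 6400 µg/day) = 0.198 (stated 0.21). Appendix E fits the prior by least squares, so a small gap is expected.

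**3. Effect of the filter on the model.** Inputs from Protocol 10.4.2 and Appendix E:

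- Model: logit(p) = log a + exp(log b) · log(d/d_max).
- Prior: ma 0.0536, sa 1.685, mb −0.1469, sb 1.001, r −0.216.
- Target interval 0.20 to 0.35. A dose is allowed only if P(rate > 0.35) is below 0.25.
- d_max: Appendix E uses 6400, but the protocol now allows 12800, so both are shown.

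Assumed data, all hypothetical: no DLT in 21 earlier subjects (6 at 200 and 3 at each of 400, 800, 1600, 3200 and 6400: 6 + 5 × 3 = 21), then 2 DLTs in 6 subjects at 12800. Schedule is ignored, and no expansion subjects are included.

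| Counted at 12800 | P(rate > 0.35 at 12800), d_max 12800 / 6400 | Model recommends |
|---|---|---|
| 2/6, both DLT subjects kept | 0.32 / 0.39 | 6400 |
| 1/5, one stopped before 90% and dropped | 0.15 / 0.20 | 12800 |
| 0/4, both stopped before 90% and dropped | 0.04 / 0.06 | 12800 |

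With 18, 21 or 32 earlier subjects and either d_max, the ranges are 0.293 to 0.386 for 2/6, 0.132 to 0.197 for 1/5 and 0.035 to 0.064 for 0/4. The recommendations do not change.

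**4. What can pull the other way.** The sensitivity set also adds expansion subjects. Taking the 1/5 case and adding 29 hypothetical expansion subjects at 6400 with 5 DLTs gives 0.27 / 0.28, and the model recommends 6400. With 3 DLTs among the 29 it recommends 12800. The filter also drops related non-DLT stops, which 10.1.2 and SAP 7.3 keep as non-events. Removing one such subject changes 2/6 to 2/5 and raises the probability from 0.32 to 0.41 (d_max 12800).

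**The case against.** The strongest reply is that the provisions that matter most already contain the exception. Dose review follows 5.1. The primary DLT analysis follows 10.1.2, SAP 7.3 and SAP 10.5.1.1. The 10.3.1 escalation block is triggered by any subject with a DLT, evaluable or not. Replacement under 3.4 is optional, and replacing a subject does not remove that subject from the SAP 7.3 set. Restart after a DLT is possible case by case (6.2.1.4.3, 6.2.1.4.4), so not every subject with a DLT falls below 90%. Protocol 2.2.4 reports about 32 subjects treated without a DLT by April 2016.

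All of this stands, and it rules out two stronger readings. A reader might infer that the main MTD estimate loses its early DLTs; SAP 10.5.1.1 uses the 7.3 set, which keeps them. A reader might also infer that the sensitivity analysis must look safer than the main one. Step 4 of the working shows that its net direction depends on the expansion data and on related non-DLT stops.

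The reply does not repair the sensitivity set, which is defined in its own words with no exception. Nor does it remove the contradiction between 3.4 or 6.2.1.3 and the analysis sets. The SAP 3.1.1 pointer can only be called a possible conflict with SAP 7.3, because the 3.4 text it was written against is not available.

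**Conclusion.** The conflict is real and should be fixed, but its reach is limited. It affects the 10.4.2 sensitivity set, replacement under 3.4, and the competing text in 6.2.1.3 and possibly SAP 3.1.1. Within the sensitivity set, the filter removes subjects whose DLT stopped dosing early and biases their contribution toward fewer DLTs. In the illustration, dropping one or two such subjects is enough to cross the 0.25 limit and change the model's recommendation.

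That size rests on hypothetical counts, the published prior and the absence of expansion data. It shows how sensitive the model is. It does not predict a decision of the dose level review team, which weighs all available data. No sample-size figure is wrong, and no data reported up to April 2016 are affected. The point matters if a DLT occurs in later cohorts, where settling the definition beforehand avoids choosing who counts after the event.

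**What to change.** Reconcile Protocol 3.4, 5.1, 6.2.1.3 and 10.1.2 and SAP 3.1.1 and 7.3 to one analysis definition. Among eligible subjects, keeping the 10.4.2 exclusions from the main analysis (subjects not naive to AMG 211 and expansion subjects in the Imaging Study), a subject is evaluable and is not replaced if either:

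- (i) a DLT occurred within the 28-day window, whatever dose was received; or
- (ii) at least 90% of the planned cycle 1 dose was received and the 28-day window was completed without a DLT.

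Part (ii) also needs 10.1.2 (completion of cycle 1) and SAP 7.3 (90% of dose) to be reconciled. Otherwise a 14-day subject lost at about day 15 counts as DLT-free after roughly half the window.

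State once how an early stop for a related non-DLT adverse event is counted. State also whether an event that the dose level review team declares a DLT outside the window (6.2.1.3) enters the model, because 10.4.2 limits the model to DLTs during the window. Point SAP 3.1.1 to the agreed definition. Add subjects with an in-window DLT to the 10.4.2 sensitivity set whatever dose they received.

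The cost is wording in both documents, with no added procedures. The protocol part is an amendment that needs IRB/IEC approval (12.1) and can go with the next one planned.

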3.5 Estimated Study Duration

The duration of this study will last approximately 2.5 years, with about 23 months for enrollment and 6 months protocol treatment period.

3.5.1 Study Duration for Subjects

It is anticipated that an individual subject will participate in the study for approximately 8 months including a screening period lasting 21 days, a treatment period lasting approximately 4 to 6 months, and a safety follow-up period lasting approximately 4 weeks. The actual duration for individual subjects will vary depending upon tolerability of AMG 211, evidence of clinical progression, and willingness to participate in the study.

In the event that a subject demonstrates clinical benefit from therapy, he or she may continue treatment with AMG 211 until he or she experiences an unacceptable adverse

event, confirmed disease progression per modified irRC ([Appendix D](#)), or he or she wishes to withdraw consent. Due to the mechanism of action of immune-enhancing therapies, subjects may experience infiltration of T cells in existing lesions leading to an apparent enlargement of existing lesions or the appearance of new lesions prior to maximal clinical benefit of AMG 211. The decision to continue on the study should be made by the treating physician and the subject.

End of study (EOS) for an individual subject is defined as the date of the final study visit (EOS visit) when safety assessments and procedures are performed. The EOS visit should occur approximately 4 weeks (+ 1 week) after the last dose of AMG 211 or at the initiation of other therapy. Subjects who complete the EOS visit will be considered to have completed the study.

3.5.2 End of Study

Primary Completion: the time when the last subject is assessed or receives an intervention for the purposes of final collection of data for the primary analysis; the primary analysis for this study will occur after all dose-escalation cohort subjects and dose-expansion cohort subjects have completed 6 months of treatment or have discontinued treatment with AMG 211.

End of Trial: the time when the last subject is assessed or receives an intervention for evaluation in the study; the final analysis will occur at this time.

4. SUBJECT ELIGIBILITY

Investigators will be expected to maintain a screening log of all potential study candidates that includes limited information about the potential candidate (eg, date of screening). Before any study-specific activities/procedure, the appropriate written informed consent must be obtained (see [Section 11.1](#)).

4.1 Inclusion Criteria

- 4.1.1 Subject has provided informed consent prior to initiation of any study-specific activities/procedures
- 4.1.2 Male or Female ≥ 18 years of age at the time of informed consent
- 4.1.3 Pathologically documented, diagnosed GI adenocarcinoma (including but not limited to esophageal, gastric, small intestine, colorectal, or pancreatic cancers) that has failed standard treatments or for which standard curative or palliative measures do not exist or are no longer effective
- 4.1.4 At least 1 measurable tumor lesion per modified irRC ([Appendix D](#))
- 4.1.5 Archival tumor tissue available or is willing to undergo biopsy of a tumor lesion before the start of treatment

4.1.6 Adequate hematological, renal, and liver function as follows:

- Absolute neutrophil count (ANC) $> 1500/\text{mm}^3 (1.5 \times 10^9/\text{L})$
- Platelet count $> 100,000 \text{ mm}^3 (100 \times 10^9/\text{L})$
- White blood cell (WBC) count $> 3 \times 10^9/\text{L}$
- Hemoglobin $> 9.0 \text{ g/dL}$
- AST and ALT $< 3.0 \times$ the upper limit of normal (ULN)
- Alkaline phosphatase (ALP) $\leq 2.5 \times$ ULN
- Total bilirubin (TBL) $< 1.5 \times$ ULN (unless subject has suspected Gilbert's syndrome or extrahepatic cause by increased indirect bilirubin fraction)
- Creatinine clearance $> 50 \text{ mL/min}$ calculated by Cockcroft-Gault
- Lipase/amylase $< 1.5 \times$ ULN
- Prothrombin time, partial thromboplastin time, and international normalized ratio (INR) $\leq 1.5 \times$ ULN

4.1.7 Life expectancy ≥ 3 months, in the opinion of the investigator

4.1.8 Karnofsky Performance Status $\geq 70\%$

4.1.9 Body weight $\geq 45 \text{ kg}$

4.2 Exclusion Criteria

4.2.1 History of allergy or reaction to any component of the AMG 211 formulation

4.2.2 Malignancy other than GI adenocarcinoma requiring current therapy

4.2.3 Evidence of uncontrolled systemic disease (other than GI adenocarcinoma)

4.2.4 Active infection or prior use of IV antibiotics for treatment of infection within 2 weeks prior to starting therapy with AMG 211

4.2.5 Corrected QT interval (QTc) ≥ 500 milliseconds at screening

4.2.6 Hepatitis B and/or C based on the following results:

- Positive Hepatitis B Surface Antigen (HepBsAg) (indicative of chronic Hepatitis B or recent acute Hepatitis B)
- Negative HepBsAg and positive Hepatitis B core antibody: Hepatitis B virus DNA by polymerase chain reaction (PCR) is necessary. Detectable Hepatitis B virus DNA suggests occult Hepatitis B.
- Positive Hepatitis C virus antibody (HepCAb) Hepatitis C virus RNA by PCR is necessary. Detectable Hepatitis C virus RNA suggests chronic Hepatitis C

